2. STUDY OBJECTIVES

Primary Objective

- To determine the **time to improvement in the 7-point ordinal scale** in patients treated with anti-IL-8 therapy compared to standard of care/controls.
 - Measured from baseline to 2 point or greater improvement in 7-point ordinal scale.

Secondary Objectives

- To evaluate the **time to death** in patients treated with anti-IL-8 therapy compared to controls.
- To evaluate the **mortality 1 month** after start of treatment in patients treated with anti-IL-8 therapy compared to controls.
- To determine the **time to intubation** in patients treated with anti-IL-8 therapy compared to controls.
 - Measured from time of disease onset to time of intubation.
- To estimate the **time to improvement in oxygenation** in patients treated with anti-IL-8 therapy compared to controls.
 - Measured as time from start of treatment until $\geq 30\%$ decrease in oxygen requirement compared to baseline
- To measure the **proportion of patients requiring ICU admission at 1 month** in patients treated with anti-IL-8 therapy compared to controls.
 - Measured as the number of patients requiring ICU admission over their hospitalization over the number of evaluable patients.
- To assess the **safety and tolerability** defined as adverse events graded by CTCAE v5.0 in patients treated with anti-IL-8 therapy compared to controls.
- To assess the **duration of hospitalization** in patients treated with anti-IL-8 therapy compared to controls.
 - Measured as time from admission to time of discharge.
- To compare the raw 7-point ordinal scale scores at day 14 in patients treated with anti-IL-8 therapy versus controls.

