5. SUBJECT SELECTION AND WITHDRAWAL

Subjects will include patients hospitalized with confirmed SARS-CoV-2 who have developed severe COVID-19. Both patients with severe disease defined as oxygen saturation $\leq 93\%$ on room air or critical disease defined as requiring non-rebreather, non-mechanical/mechanical ventilation, high-flow nasal cannula, or ICU admission will be recruited. Subjects will be identified and recruited through inpatient units at NYP/Columbia University Irving Medical Center.

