5.1 Inclusion Criteria

- Male or female adult ≥ 18 years of age at time of enrollment.
- Confirmed diagnosis of SARS-CoV-2 infection ≤ 14 days prior to registration.

- Inpatient hospitalization (or documentation of a plan to admit to the hospital if the patient is in the emergency department)
- Evidence of pneumonia by chest radiographs, chest CT **OR** chest auscultation (rales, crackles).
- Severe respiratory disease (oxygen saturation $\leq 93\%$ on room air or requires $\geq 2\text{L}$ oxygen by NC in order to maintain $\text{SaO}_2 \geq 93\%$) **OR** critical respiratory disease (requiring non-rebreather, non-mechanical/mechanical ventilation, high-flow nasal cannula, ICU admission).
- Patients can continue their anti-cancer therapy at the discretion of the treating physician.
- *Adequate laboratory tests including:*
 - ANC $>500 \text{ cells/mm}^3$
 - Platelet count $>20,000 \text{ cells/mm}^3$
 - Serum total bilirubin $<1.5 \times \text{ULN}$
 - ALT $<5 \times \text{ULN}$
 - AST $<5 \times \text{ULN}$
- *Age and Reproductive Status*
 - a) Males and females, aged at least 18 years old
 - b) Women of childbearing potential (WOCBP) must have a negative serum or urine pregnancy test (minimum sensitivity 25 IU/L or equivalent units of human chorionic gonadotropin) within 24 hours prior to the start of study treatment.
 - c) Women must not be breastfeeding.
 - d) WOCBP must agree to follow instructions for method(s) of contraception for the duration of study treatment plus for a total of 155 days post treatment completion. Local laws and regulations may require use of alternative and/or additional contraception methods.
 - e) WOCBP who are continuously not heterosexually active are also exempt from contraceptive requirements, but should still undergo pregnancy testing as described in this section.
 - f) Males who are sexually active with WOCBP must agree to follow instructions for method(s) of contraception during study treatment with BMS-986253 for a total of 215 days post-treatment completion.
 - g) Azoospermic males are exempt from contraceptive requirements. WOCBP who are continuously not heterosexually active are also exempt from contraceptive requirements, and still must undergo pregnancy testing as described in this section.
- Willingness to provide written informed consent and HIPAA authorization for the release of personal health information, and the ability to comply with the study requirements

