5.2 Exclusion Criteria

- Treatment with anti-IL-6, anti-IL-6R antagonists or Janus kinase inhibitor (JAKi) within 48 hours of first dose of study treatment.
- No other investigational therapies as part of another clinical trial with the intent to treat the patient's COVID-19 can be administered while the patient is enrolled in the study.
 - Exception is remdesivir, hydroxychloroquine, convalescent plasma or other treatments being used as compassionate use or under Emergency Use Authorization (EUA) for COVID-19 per Investigator discretion.
- Expected non-COVID-related survival of < 2 months.
- Receipt of non-oncology vaccines containing live virus for prevention of infectious diseases within 4 weeks prior to first dose of study treatment
- History of severe hypersensitivity reaction to any mAb
- Multi-organ failure requiring vasopressors or continuous veno-venous hemofiltration (CVVH) or extracorporeal membrane oxygenation.
- No active systemic bacterial or fungal infection
 - Excludes patients with positive blood cultures not infections like empiric pneumonia, antibiotic coverage, UTIs, etc.
 - Patients with a history of positive bacterial or fungal cultures but on enrollment do not have suspected or known active systemic bacterial or fungal infections are permitted.

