11.2 Secondary Endpoints

11.2.1 *Time to death*

The time to death will be defined as the time from onset from symptoms until death from any cause. Patients who are alive or lost to follow-up at the cut-off date will be censored from this analysis.

11.2.2 *Mortality at 1 month*

1-month mortality is defined as the percentage of patients who have died 1 month from the time of start of treatment.

11.2.3 *Time to intubation*

The time to intubation will be defined as the time from symptom onset until time of intubation. Any patients already intubated at enrollment will be censored from this analysis.

11.2.4 *Time to improvement in oxygenation*

The time to improvement in gas exchange will be defined as the time from time of start of treatment until a $\geq 30\%$ decrease in oxygen requirement compared to

baseline [or elimination of oxygen requirement] without a decrease in SpO2 sustained for at least 48hrs or until discharge.

11.2.4 *Proportion of patients requiring ICU admission at 1 month.*

The proportion of patients requiring ICU admission will be calculated as the number of patients requiring ICU admission over the course of their hospitalization over the number of evaluable patients.

11.2.5 *Safety and Toxicity*

All subjects receiving at least one dose of the study drug will be evaluated for safety by monitoring symptoms, physical examinations, and laboratory tests. Adverse events will be classified and graded according to the NCI Common Toxicity Criteria version 5.0 (see Appendix A). The absolute number and frequency of each adverse event will be reported, and subdivided according to toxicity grade. A description of adverse events by treatment arm will also be reported. A particular adverse event occurring more than once in the same subject will be counted only once and at its worse grade.

11.2.6 *Duration of Hospitalization*

Duration of hospital admission will be measured from the time of admission until the time of discharge.

11.2.7 *7-point Ordinal Scale Score*

The mean/medians of the 7-point ordinal raw scores at day 14 from the start of treatment will be computed and compared between the treatment and control groups.

Exploratory Endpoints.

11.2.8 *Change in inflammatory markers from baseline*

Changes in LDH, D-Dimer, CRP, ESR, NLR and absolute lymphocytes before and after treatment and over time will be measured every other day during hospitalization.

11.2.9 *Change in circulating sIL-6 levels from baseline*

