13 STATISTICAL CONSIDERATIONS

13.1 Study Design and Sample Size

This study is a single-center, randomized open-label phase 2 trial to evaluate the efficacy and safety of anti-IL-8 in hospitalized adults with severe or critical COVID-19. The primary endpoint is time to improvement in clinical status: the time (days) required from the start of treatment to the improvement of clinical status (2 points) assessment from baseline based on the 7-point ordinal scale. Patients for whom there was no event will be censored.

Patients will be randomized in a 2:1 allocation ratio to either anti-IL-8 or standard of care. Patients will be assessed daily while hospitalized. Discharged patients will be contacted by telephone on Day 29 and then monthly up to one-year to assess status. In addition to these specific assessment times, one interim analysis is planned at and the DSMC will actively monitor interim data to make recommendations about early signs of overwhelming efficacy and futility/study closure (see Section 13.4.)

With a sample size of 138 patients: N=92 patients randomized to the treatment arm and N=46 patients assigned to the standard of arm/control, the study will have 80% power to detect an increase in median time to improvement from 2 days (control) to 5 days (treatment arm) with one-sided alpha of 0.025. The sample size was estimated based on a hazard ratio (HR) of 0.40 assuming an exponential survival distribution with inflation to account for one interim look and 5% drop-out rate.

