13.2 Study Endpoints and Analysis Plan

All subjects who receive at least one dose of study drug will be considered evaluable and included in the efficacy and safety analysis.

Analytic plan for primary objective:

The primary efficacy null hypothesis of the equality of time to improvement (2 points) in clinical status curves will be tested with the log-rank test. The overall type I error for the primary analysis will be considered one-sided alpha of 0.025. Kaplan-Meier estimates will be reported for each of the two arms with median time to improvement and 95% confidence intervals (CI). Cox regression will be employed to estimate the treatment effect (HR) and 95% CI.

Analytic plan for secondary and exploratory objective:

We will estimate the distributions of all time-to-event endpoints using the Kaplan-Meier method and if possible, provide medians (95% CI). Comparisons between survival curves will be assessed using log-rank tests and Cox regression models.

For each arm, we will estimate the 1-month mortality rate and incidence of adverse events graded by CTCAE v5.0 using the exact 95% confidence intervals. Comparisons between the two arms will be assessed using chi-squared or Fisher's exact tests. The mean/medians of the 7-point ordinal scores at day 14 after the start of treatment will be computed and compared between the two groups using two-sample t-test or the equivalent non-parametric Wilcoxon Rank-Sum test if normality is not satisfied.

Changes in exploratory endpoints (before and after treatment) will be quantified using means (95% CI) and/or medians (inter-quartile ranges) for non-normal data. Comparisons between the two arms will be made using two-sample independent t-tests or the non-parametric equivalent, Wilcoxon Rank-Sum test. The associations between baseline levels and/or changes over time of IL-8 and other key cytokines (TNF, IL-1b, IL-6) with outcomes will be assessed using regression models.

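### The ICU-admission endpoint counts patients already in ICU at entry, which dilutes the treatment contrast in a secondary endpoint

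*Combined protocol and SAP*

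**What the plan says.** The endpoint is the second of two items numbered 11.2.4 in section 11.2. Its title refers to ICU admission at one month, but its text is "the number of patients requiring ICU admission over the course of their hospitalization over the number of evaluable patients". Section 2 repeats the definition ("Measured as the number of patients requiring ICU admission over their hospitalization over the number of evaluable patients"), and so does the synopsis.

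Eligibility allows patients who are in ICU at entry. Section 5.1 accepts "critical respiratory disease (requiring non-rebreather, non-mechanical/mechanical ventilation, high-flow nasal cannula, ICU admission", and section 5 says that patients with critical disease, including "high-flow nasal cannula, or ICU admission will be recruited". Section 5.2 excludes some of the sickest patients: "Multi-organ failure requiring vasopressors or continuous veno-venous hemofiltration (CVVH) or extracorporeal membrane oxygenation". Other ICU patients remain eligible.

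The denominator is set in section 13.2: "All subjects who receive at least one dose of study drug will be considered evaluable and included in the efficacy and safety analysis". Baseline ICU status plays no part in it.

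Time to intubation, in the same section 11.2, does deal with patients who have the event at entry: "Any patients already intubated at enrollment will be censored from this analysis". The ICU endpoint has no matching rule.

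**The concern.** A hospitalization begins before randomization, so a window covering the whole stay takes in ICU admissions that came before any study treatment. A patient in ICU at entry meets the endpoint as worded, and treatment cannot alter that. These patients add the same expected proportion of events to both arms. The observed difference moves toward zero and variance is added that has nothing to do with the drug.

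What is at stake is how this secondary endpoint can be read. A small or null difference could mean that the drug does not prevent ICU admission, or that part of the outcome was settled before dosing. The primary endpoint, its sample size and its interim boundaries are not affected.

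**Working it through.** **Inputs from the documents.** Arm sizes are in section 13.1: "N=92 patients randomized to the treatment arm and N=46 patients assigned to the standard of arm/control". Section 7.5 gives 2:1 randomization and describes no stratification. The plan states no ICU rate, effect size, power or baseline ICU share for this endpoint, so there is no figure of its own to reproduce.

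**Assumptions.** These are f (the share in ICU at baseline, equal in expectation in the two arms), the new-admission rates p_c (control) and p_t (anti-IL-8) among patients not in ICU at entry, and Fisher's exact test at two-sided 5%. Section 13.2 names chi-squared or Fisher's exact tests for 1-month mortality and adverse events. It names no test for the ICU proportion.

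**Step 1, dilution.** As worded, an arm's expected proportion is f + (1-f)p. Subtracting the arms gives

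RD = [f + (1-f)p_c] - [f + (1-f)p_t] = (1-f)(p_c - p_t).

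This holds for any rates. Examples:

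- f=30%, 40% versus 15%: 0.30 + 0.70×0.40 = 58.0% and 0.30 + 0.70×0.15 = 40.5%. The 25-point difference becomes 17.5 points.
- f=30%, 40% versus 20%: 58.0% and 44.0%. The 20-point difference becomes 14 points, and the risk ratio moves from 0.50 to 0.76.
- f=30%, 30% versus 20%: 51.0% and 44.0%. The 10-point difference becomes 7 points.
- f=5%, 40% versus 15%: 43.0% and 19.25%. The difference is 23.75 points.

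**Step 2, power.** Restriction keeps the full difference but uses fewer patients: at f=30%, about 0.70×92 = 64 and 0.70×46 = 32. Simulated power is:

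| New admissions, control vs anti-IL-8 | f | As written | Restricted |
|---|---|---|---|
| 40% vs 15% | 5% | 81% | 87% |
| 40% vs 15% | 20% | 60% | 79% |
| 40% vs 15% | 30% | 47% | 72% |
| 40% vs 15% | 40% | 37% | 65% |
| 40% vs 20% | 30% | 33% | 51% |
| 30% vs 20% | 30% | 12% | 16% |

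Exact enumeration, with the at-risk numbers set at their expected values, agrees to within about 2 points in every row. Restriction gains power in each case, but the gain is small when f is small or the effect is modest.

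**Step 3, chance imbalance and type I error.** At f=30% the standard deviation of the between-arm difference in baseline ICU share is √[0.30×0.70×(1/92 + 1/46)] = 0.083, about 8 points. That is noise carried straight into the endpoint. With 40% new admissions in both arms, the rejection rate of the endpoint as written is 3.9% to 4.6% for f from 5% to 40%, below the nominal 5%.

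**The case against.** The strongest counter-arguments are these.

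- **The window is ambiguous.** The title and the objective speak of one month, which could mean ICU status at that time, or events by then counted from start of treatment. On a status reading the outcome would not be fixed before treatment. The conflict is real. However, the only operational definition, given in three places, counts the whole hospitalization, and the dilution follows from that text.
- **Baseline ICU share may be low.** Section 5.2 removes multi-organ failure on vasopressors, CVVH or ECMO. At f=5% the loss is only about 6 points of power. This stands: the documents do not allow f to be fixed.
- **The power gain depends on a large effect.** For 30% versus 20% the endpoint is underpowered either way. This stands too.
- **The severity subgroup helps.** In section 13.3, ICU patients fall in the critical group, so the severe group should contain none. This is partial mitigation only. The analysis is labelled post hoc, the severity split does not say which endpoints it covers, and the critical group mixes ICU patients with patients on a non-rebreather or high-flow oxygen.
- **It is one secondary endpoint** with no power claim and no decision rule. This is correct and limits the importance of the point.

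A reader might also infer that a chance imbalance in baseline ICU patients would produce a spurious treatment effect. The plan does not support that. Randomization balances the share in expectation, and the test allows for chance variation, as the null rejection rates show.

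**Conclusion.** The point holds as dilution and loss of precision in a secondary endpoint. As worded, patients in ICU at entry are events in both arms, and the risk difference is multiplied by exactly (1-f). That much follows from the definition together with the eligibility criteria, given a common f. The consequence for power depends on assumed values of f, admission rates, test and alpha. Over the scenarios shown, the loss against a restricted analysis runs from about 4 points (30% versus 20%, f=30%) to about 28 points (40% versus 15%, f=40%).

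The documents do not support a claim of bias or inflated type I error, nor a claim that restriction would make this endpoint well powered in general. A correction is worthwhile because the protocol already applies the same idea to intubation and the edit is small.

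**What to change.** In section 11.2.4, the synopsis and section 2, define the endpoint as new ICU admission from randomization through day 28 among patients not in ICU at randomization, analysed as randomized. Start of treatment could be the origin instead, in line with the 1-month mortality endpoint, but the text should then say which date applies to controls. Restricting on a status fixed before randomization keeps the randomized comparison intact, and the fixed window reconciles the one-month title with the text.

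State the denominator explicitly rather than relying on the evaluable definition, since a rule based on receiving study drug, read literally, leaves out the control arm. Report the number in ICU at baseline by arm. Report deaths without ICU admission alongside, or count them as events in a sensitivity analysis, because otherwise such a death would be scored as a favourable outcome.

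The cost is matching edits in three places and a smaller denominator for this endpoint. Sections 7.7 and 10.3 already plan an assessment 28 days after start of treatment, so little or no new data collection should be needed.

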3. BACKGROUND

3.1 Disease Background

Coronavirus disease 2019 (COVID-19) represents an emerging public health crisis that is caused by infection with the novel coronavirus, severe acute respiratory syndrome coronavirus 2 (SARS-CoV-2), which is associated with high transmissibility and mortality.¹ The World Health Organization (WHO) has defined COVID-19 as a pandemic. Symptoms include fever, cough, myalgias, shortness of breath and are most commonly mild in severity. However approximately 14% of patients with COVID-19 will develop severe disease (defined as dyspnea, respiratory frequency ≥ 30 /minute, blood oxygen saturation $\leq 93\%$, PaO₂/FiO₂ ratio < 300 , and/or lung infiltrates $> 50\%$ of the lung field within 24-48 hours).² Although the overall mortality appears $< 1\%$, patients with severe disease have a mortality of approximately 20-25% across multiple studies reported to date.³⁻⁵ Medical co-morbidities also appear associated with particularly poor outcomes.³ Particular, in cancer patients, reports suggest a mortality as high as 7%. Cancer patients also appear to have a dramatically increased rate of severe events (invasive ventilation or

death), with a rate of 40% in a small study from China.⁶ Novel strategies to address respiratory failure in COVID patients generally and cancer patients in particular represents an urgent and critical need.

Figure 1 Clinical Course of Patients with COVID-19

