11. MEASUREMENT OF EFFECT

11.1 Primary Endpoint

11.1.1 *Time to improvement (2 points) in 7-point ordinal scale*

The time to improvement (2 points) will be defined as the time (days) required from the start of treatment to the improvement of clinical status (2 points) assessment from baseline based on the 7-point ordinal scale. Patients for whom there was no event will be censored from this analysis. 7-point ordinal scale will be calculated as follows: (1) death, (2) hospitalized on invasive mechanical ventilation or extracorporeal membrane oxygenation, (3) hospitalized, requiring non-invasive ventilation or high flow nasal cannula, (4) hospitalized, requiring supplemental oxygenation (5) hospitalized, not requiring supplemental oxygenation and requiring ongoing medical care (COVID-19 related or otherwise) (6) Hospitalized, not requiring supplemental oxygen – no longer requires ongoing medical care, (7) not hospitalized.

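### Duration of hospitalization has no rule for in-hospital death; Kaplan-Meier with deaths censored would overstate discharge and make a purely life-saving drug look neutral on this endpoint

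*Combined protocol and SAP*

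**What the plan says.** Section 11.2.6 defines the endpoint: "Duration of hospital admission will be measured from the time of admission until the time of discharge". The synopsis and Section 2 use the same clock ("Measured as time from admission to time of discharge"). None of the three places mentions death in hospital.

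Section 13.2 does not name this endpoint. It says "We will estimate the distributions of all time-to-event endpoints using the Kaplan-Meier method", and then "Comparisons between survival curves will be assessed using log-rank tests and Cox regression models". No other method in that section fits a duration that some patients never complete, so the endpoint falls under this sentence by inference.

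Other endpoints do carry a censoring rule. For the primary endpoint, Section 11.1.1 states "Patients for whom there was no event will be censored from this analysis", without saying at what time. Time to death and time to intubation have rules of their own. Duration of hospitalization has none.

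On how common death may be, Section 3.1 reports that "patients with severe disease have a mortality of approximately 20-25% across multiple studies".

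**The concern.** A patient who dies in hospital has no discharge time. Death prevents discharge, and treatment may change its frequency, so it cannot be treated as uninformative censoring. If the cited 20-25% applied to all 138 patients, 138 × 0.20 = 27.6 to 138 × 0.25 = 34.5, or roughly 28 to 35 patients, would never be discharged alive.

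The analyst could censor these patients at death, count death as the end of stay, drop them, or keep them as never discharged. The plan picks none of these, and the choice decides the sign of the treatment effect whenever mortality differs between arms. In an open-label trial that choice should not be left until the data are in hand.

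**Working it through.** The documents give no figure for this endpoint, so there is none to reproduce. The 41 events and hazard ratio of 0.40 belong to the primary endpoint and do not bear on the point.

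**Inputs from the documents.** Control mortality of 20% or 25% (Section 3.1, used here as in-hospital mortality); arms of 92 and 46 (Section 13.1).

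**Assumptions not in the documents.** The drug halves mortality (20% to 10%, or 25% to 12.5%). It does not slow discharge in anyone who would have survived anyway. Median time to discharge is 10 days with deaths censored, and the horizon is 100 days. A second scenario gives rescued patients a long stay, with a median of about 25 days.

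**Step 1: what Kaplan-Meier estimates when deaths are censored.** Take a constant discharge hazard λ, equal in both arms, and a death hazard λm/(1−m), where m is in-hospital mortality. With λ = ln 2/10:

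- One minus Kaplan-Meier at day 100 is 1 − 2^(−10) = 99.9%, in both arms and whatever the mortality.
- The cumulative incidence of live discharge at day 100 is (1−m) × (1 − 2^(−10/(1−m))). This gives 80.0% for m = 0.20, 90.0% for m = 0.10, 75.0% for m = 0.25 and 87.5% for m = 0.125.

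So Kaplan-Meier overstates control-arm discharge by about 20 to 25 percentage points and shows none of the 10 to 12.5 point gain.

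**Step 2: discharge hazard ratio under each convention (above 1 favours the drug).** Closed form for constant hazards:

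- Deaths censored: λ/λ = 1.
- Death as end of stay: the exit hazard is λ/(1−m), so HR = (1−mC)/(1−mT), with mC and mT the control and treated mortality. This is 0.80/0.90 = 0.889 and 0.75/0.875 = 0.857. A smaller assumed reduction, 25% to 20%, would give 0.75/0.80 = 0.94.
- Deaths dropped: survivors' stays also have hazard λ/(1−m), so the ratio is the same.

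Simulation (600,000 patients for each hazard ratio) for the 20% and 25% control rates:

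| Handling of in-hospital death | Constant hazards | Rescued patients stay long |
|---|---|---|
| Censored at death | 1.00, 1.00 | 0.97, 0.97 |
| Counted as end of stay | 0.89, 0.86 | 0.87, 0.83 |
| Dropped | 0.89, 0.86 | 0.86, 0.83 |
| Kept as never discharged | 1.24, 1.30 | 1.22, 1.28 |

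With mortality of 25% in both arms, every row gives 1.00. The differences therefore come only from how death is handled.

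**Step 3: at the planned size (4,000 simulated trials of 92 versus 46 in each scenario).**

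- Censored at death: significant for the drug (one-sided p < 0.025) in about 2% of trials, which is chance level.
- Death as end of stay: the estimate goes against the drug in 75-85% of trials, and significantly so in 10-18%.
- Kept as never discharged: significant for the drug in 17-24%, and significantly against it in 0.4% or fewer.

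**The case against.** Several counter-arguments have force.

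- **The method is inferred.** Section 13.2 never assigns Kaplan-Meier to this endpoint by name. That stands. It is nonetheless the only listed method that fits, and no alternative that accounts for death is offered.
- **The drug would look harmful.** A reader might infer that the planned analysis would turn a life-saving drug into an apparently harmful one. The documents do not support that. With deaths censored, the result is about neutral (0.97-1.00). The clearly adverse values need death counted as the end of stay or deaths dropped. The plan states neither, and it equally does not exclude keeping deaths as never discharged, which gives the right sign.
- **Censoring deaths is not invalid as such.** Log-rank and Cox with deaths censored legitimately compare discharge rates among patients still in hospital. The error lies in reading one minus Kaplan-Meier as the probability of discharge, or the neutral ratio as no effect on leaving hospital alive.
- **Death is analysed elsewhere.** Time to death ("The time to death will be defined as the time from onset from symptoms until death from any cause"), 1-month mortality and the day-14 ordinal score, whose lowest category is death, would all show a survival benefit. This endpoint has no allocated alpha or power and does not enter the interim boundaries.
- **The admission clock.** It may look like a source of bias, because days before randomization are counted. Randomization balances those days in expectation, so they add noise and not bias between arms.
- **The inputs.** The 20-25% is a background literature figure and not a design assumption. The halving of mortality and the lengths of stay come from outside the documents.

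**Conclusion.** The point holds for this one secondary endpoint. The handling of in-hospital death is unspecified, and the method that applies by default has no place for it. Censoring deaths would overstate discharge and remove any gain that comes through survival. The adverse values of 0.83-0.89 are illustrative of other readings the plan leaves open; they are not a prediction of what the sponsor will do. All hazard ratios assume halved mortality from a 20-25% control rate. Under constant hazards, the results for censoring deaths and for counting them as the end of stay do not depend on the assumed length of stay. The trial's conclusion on mortality is not at risk.

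**What to change.** In Sections 2, 11.2.6 and 13.2 and the synopsis:

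- Define the endpoint as time to discharge alive. Treat in-hospital death as a competing event, so that a patient who dies counts as never discharged.
- Report the cumulative incidence of live discharge by arm, with Gray's test or a subdistribution hazard ratio.
- Prespecify a follow-up horizon long enough to cover stays beyond day 29. A day-28 cut-off would truncate stays that the plan itself anticipates, since Section 7.1 provides for patients still hospitalized at day 29.
- As a secondary refinement, start the clock at randomization, close to the primary endpoint's start-of-treatment origin. This removes days that treatment cannot affect.

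The cost is wording only. The daily ordinal score already records death and discharge (Section 10), an assessment about 28 days after start of treatment is scheduled whether or not the patient has been discharged (Section 7.7), and survival is sought for at least a year (Section 5.5.2). The one loss is that the estimate is no longer total length of stay, which can be reported descriptively. The corrected analysis would still have only about 17-24% power under the assumptions above and should be presented as supportive.
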